#### Aims:

1. To evaluate any changes in pain relief in the 2nd and 3rd year of deep brain stimulation (DBS) in the midbrain periaqueductal/periventricular gray (PAG/PVG).
2. To assess needs for changes in stimulation parameters (contact selection, voltage, frequency, pulse width) to continue optimal relief.
3. To determine changes in injury status revealed by the ASIA score.
4. To uncover later-occurring adverse effects.

Enrollment. Subjects will preferably continue without a gap at the end of the original 52 week study. However, they may be enrolled at any time during the extension to accommodate the time needed to obtain regulatory approval for the extension or subjects who wish to take a break. An additional informed consent form will be used for enrollment.

Procedures. Subjects will receive continuous DBS in the PAG/PVG from the previously implanted system. They will return every 12 weeks to the study site to optimize the stimulation parameters for pain control. The optimum may drift or may not have been determined previously from the very large range of possible settings. Subjects will leave the visits with a blinded choice of settings (2 to 4, labeled A, B, C D), which they can explore at home. Preliminary findings suggest that pain changes over several days when settings are changed, and that slow recursive testing is the best way to find the optimum. Subjects may request visits

at other times for stimulation adjustment or other study related issues. Some later subjects may have a PC+S generator device implanted, which allows recording from the stimulating leads. Subjects with this device will also undergo brief recording sessions during visits, following the protocol of the first year.

Tests and questionnaires. The study extension will use only questionnaires and study forms from the original study. It will omit autonomic system testing and quantitative sensory testing. On-site assessment will be done in clinical exam rooms and offices of the Miami Project to Cure Paralysis of the University of Miami Miller School of Medicine, including ASIA assessment. If the stimulator settings are producing consistent adequate pain relief, visits may be omitted at the subject's discretion, except for weeks 104 and 156, and assessments will be made by telephone questionnaire.

The following will be assessed every 12 weeks.

- International Spinal Cord Injury pain basic data set (ISCI)
- Neuropathic Pain Symptom Inventory (NPSI)
- Beck depression inventory (BDI)
- Guy-Farrar patient global impression of change (PGIC)
- Medication usage

In addition, subjects will be asked to keep a pain diary with a morning and evening pain score rated from 0 (no pain) to 10 (worst ever pain). The pain diary will be retrieved at the visits or by telephone.

At weeks 104 and 156, we will determine the ASIA score (American Spinal Injury Association neurological examination, sensory and motor). On week 156, an open ended qualitative exit interview will be conducted with audiovisual recording, including questions on the overall experience, effects on daily life, etc.

Adverse events (AEs) will be recorded immediately after telephone contact by the subject (subject-reported AEs) and during visits to the study site (clinician-reported AEs).

• **Table 1: List of Procedures for planned study**

Screening:	
1	Urine pregnancy test
2	HIV, HBV, HCV testing
3	Laboratory tests (CBC, CMP, BSCP, prothrombin time test)
4	Medical history, Brief neurological and medical examination
5	Autonomic dysreflexia assessment
6	Spinal Cord Injury history
7	ASIA motor / sensory scores
8	Functional and pain assessments
9	Psychological Assessment (MMSE, BDI)
10	Drug abuse screening test
Baseline Procedures (at 2- weeks):	
1	Autonomic dysreflexia assessment
2	Functional and pain assessments
3	Psychological Assessment (MMSE, BDI)
4	ASIA motor / sensory scores
5	Medical history, Brief neurological and medical examination
6	Patient diary on medications
DBS Device Implantation Surgical Procedure:	
1	Initial MRI / CT scan of the spine
2	Chest X-ray; Electro-cardiogram
3	1-Targeting & Lead placement: at 7-week
3	2-DBS & Lead connection: at 8-week
ICU Monitoring/Medical Treatment:	
1	Blood Pressure Monitoring
2	Oxygenation
3	Additional physiological monitoring specific to subject (displayed on telemetry monitor)
4	Laboratory tests (CBC, CMP, BSCP, prothrombin time test)
5	Post op medications (antibiotics, DVT prophylaxis, etc.)
Follow-Up Procedures:	
1	Long-term DBS in PAG/PVG starting on week 8
2	Telephone interview: weekly, except on-site visit weeks, from week 3
3	Pain assessments: on even weeks, starting on week 10
4	Autonomic Standards Assessments: on on-site visit weeks
5	Tilt table response exam: at 20-week, 32-week, and 52-week
6	Beck Depression Inventory: on visit weeks
7	Folstein Mini-Mental State exam: at 20-week, 32-week, and 52-week
8	Patient Global Impression of Change: weekly, starting on week 9
9	ASIA motor and sensory assessments: at 20-week, 32-week and 52-week.
10	Qualitative exit interview at 52 weeks

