### 12.6.1 Extension of study

Introduction. The study will be extended for approximately 2 more years, precisely 104 weeks. The purpose is to obtain long-term follow-up information on safety and efficacy, in subjects that have opted to receive continuing brain stimulation. We label weeks in terms of original enrollment. Thus the surgery occurs in weeks 7 and 8 and the original study finishes in week 52, with the extension lasting from week 53 to week 156.

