#### 5. Recording and Reporting

5.1. At each required study visit, all AEs that have occurred since the previous visit must be documented and recorded in the Adverse Event Record of the patient's CRF. The information recorded should be based on the signs or symptoms detected during the physical examination and clinical evaluation of the patient. In addition to the information obtained from those sources, the patient should be asked the following nonspecific question: "How have you been feeling since your last visit?" Signs and symptoms should be recorded using standard medical terminology.

5.2. The following AE information must be included (when applicable):

- the specific condition or event and direction of change;
- whether the condition was preexisting (i.e., an acute condition present at the start of the study or history of a chronic condition) and, if so, whether it has worsened (e.g., in severity and/or frequency);
- the dates and times of occurrence; severity; causal relationship to study device; action taken; and outcome.

5.3. The causal relation between an AE and the study device will be determined by the investigator on the basis of his or her clinical judgment and the following definitions:

- **Definitely related:** Event can be fully explained by use of the study device.
- **Probably related:** Event is most likely to be explained by use of the study device rather than the patient's clinical state or other agents/therapies.
- **Possibly related:** Event may be explained by use of the study device or by the patient's clinical state or other agents/therapies.
- **Probably not related:** Event is most likely to be explained by the patient's clinical state or other agents/therapies, rather than the study device.
- **Definitely not related:** Event can be fully explained by the patient's clinical state or other agents/therapies.

5.4. When assessing the relationship between use of a study device and an AE, the following should be considered:

- Temporal relationship between use of the study device and the AE.
- Biological plausibility of relationship.
- Patient's underlying clinical state or concomitant agents and/or therapies.

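### In the extension, how often subjects are asked about adverse events depends on their pain relief: as written, the longest gap is 12 weeks for a subject who attends every visit and 52 weeks for one who omits the optional visits

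*Combined protocol and SAP*

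**What the plan says.** Section 12.6.1 extends follow-up, "with the extension lasting from week 53 to week 156". Its fourth aim is "To uncover later-occurring adverse effects".

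- **Visits.** "They will return every 12 weeks to the study site to optimize the stimulation parameters for pain control". The relaxation is: "If the stimulator settings are producing consistent adequate pain relief, visits may be omitted at the subject's discretion, except for weeks 104 and 156", after which the sentence continues "and assessments will be made by telephone questionnaire".
- **Content of the 12-weekly assessment.** The list is ISCI, NPSI, BDI, PGIC and medication usage. It has no AE entry.
- **AE recording.** In the extension, AEs are to be "recorded immediately after telephone contact by the subject (subject-reported AEs) and during visits to the study site (clinician-reported AEs").
- **General AE rule.** Appendix 1, item 5.1 requires AEs arising after one visit to be documented at the next required visit, where "the patient should be asked the following nonspecific question". It gives no such rule for a scheduled call.
- **Entry.** Continuing without a break is preferred, but "they may be enrolled at any time during the extension".
- **First 52 weeks.** In Table 2 the AE assessment row is marked in the post-implantation telephone-interview columns as well as at the site visits.

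**The concern.** Whether a subject may skip visits is decided by pain relief, which is the efficacy outcome. Skipping a visit also removes the only scheduled occasion on which the extension text provides for AEs to be sought. Subjects doing well on pain are therefore asked about harms less often than subjects doing badly, in a phase that exists partly to find late harms.

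Section 10 lists erosion through the skin, hardware migration, delayed infection, and battery or mechanical failure as possible throughout the study. Some of these may be noticed by a clinician before the subject reports them, and brief events may be forgotten over a long interval. With at most 12 subjects, one or two uncaptured events would visibly change a reported rate. Section 17.1 compares AE incidence with historical controls. The documents do not say whether extension events enter that comparison; if they do, thinner ascertainment would push the comparison in the favourable direction.

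**Working it through.** **Inputs.** From Section 12.6.1: extension weeks 53 to 156, a 12-week visit interval, and mandatory visits at weeks 104 and 156. From Section 12.6: the last assessment of the initial study is at week 52. Assumption: the 12-week grid is counted from week 52.

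**Plan's own figure.** 156 − 53 + 1 = 104 weeks, which matches the stated length.

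**Visit counts and gaps**

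- Grid visits: weeks 64, 76, 88, 100, 112, 124, 136, 148, which is 8 visits. Weeks 104 and 156 are not on this grid, so full attendance is up to 8 + 2 = 10.
- Full attendance, gaps from week 52: 12, 12, 12, 12, 4, 8, 12, 12, 12, 8 (sum 104). The longest is 12 weeks.
- All optional visits omitted: weeks 104 and 156 only. Gaps 52 and 52.

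**Mean wait from onset to the next visit**, for an onset uniform over the extension, is Σg² / (2Σg), where g is a gap:

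- Full attendance: (7×144 + 16 + 2×64) / (2×104) = 1152 / 208 = 5.5 weeks.
- Mandatory visits only: (2×2704) / 208 = 26 weeks.

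**Illustration with assumed event durations.** The probability that an event lasting d weeks is present at some visit is c = Σ min(g, d) / 104.

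| d (assumed) | Full attendance | Mandatory visits only |
|---|---|---|
| 4 weeks | 40/104 = 0.38 | 8/104 = 0.08 |
| 8 weeks | 76/104 = 0.73 | 16/104 = 0.15 |

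Let s be the fraction of events about which the subject telephones (assumed). The recorded share is then s + (1 − s)c. For an 8-week event:

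| s (assumed) | Full attendance | Mandatory visits only |
|---|---|---|
| 0 | 0.73 | 0.15 |
| 0.5 | 0.5 + 0.5×0.731 = 0.87 | 0.5 + 0.5×0.154 = 0.58 |
| 1 | 1.00 | 1.00 |

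These shares ignore recall at weeks 104 and 156, and anything volunteered during the telephone questionnaire. They mark the unfavourable end and are not an estimate of the bias.

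**The case against.** The strongest reply is that AE enquiry by telephone is already this trial's practice. Table 2 marks it at post-implantation telephone weeks, and Section 12.6.1 says that the extension reuses the earlier questionnaires and forms. The AE sentence names two routes without excluding others, and the 12-weekly list may omit AEs simply because it is a list of instruments. This may well be what was intended, and it shows that the remedy is workable. It does not settle the text: the extension has its own assessment list and its own AE sentence, and neither puts an AE question into the call.

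Other safeguards are real. Subjects may request visits, can reach study staff at any hour (Section 10.1), and give BDI, PGIC and medication data every 12 weeks even by telephone. Serious events have a 24-hour reporting rule once the investigator knows of them. Weeks 104 and 156 give a catch-up under item 5.1. These limit the loss, but they are either spontaneous reporting, indirect, or late, so they do not equalise scheduled questioning.

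A reader might infer four stronger things that the documents do not support:

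- **That harms in subjects with good relief go unrecorded.** The catch-up visits and subject-initiated contact contradict this.
- **That nothing collects AEs for someone who joins late or after a break.** Item 5.1 reaches back to the previous visit, and item 3.1 keeps a subject within the reporting window until 30 days after the last stimulation.
- **That subjects with good relief receive the most sustained stimulation.** Section 12.6.1 gives continuous stimulation to all.
- **That telephone scoring is a new flaw in the pain data.** The first 52 weeks already mix telephone and on-site pain scores.

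Nor does the plan compare AE rates between subjects with and without relief, and Section 17.1 describes the safety analysis as mainly descriptive.

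**Conclusion.** The point holds as a defect in the written plan. Scheduled AE questioning in the extension is conditional on the efficacy outcome, with up to 10 visits against 2 and a longest gap of 12 weeks against 52. These figures are the two extremes: they assume a grid counted from week 52, a subject who uses every permitted omission, and calls made exactly as the list describes. Omission is optional, so actual follow-up may lie anywhere between them.

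The likely consequence is late and partial capture of events that are transient or that the subject does not notice, and a late AE rate that is somewhat too low. How much too low depends on event duration, willingness to telephone, and recall, none of which the documents give. The plan should be amended, because the affected quantity is a stated extension aim and the remedy is cheap. The matter does not touch the 52-week results.

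**What to change.** Amend the AE sentence and the 12-weekly list in Section 12.6.1 so that the open question in Appendix 1, item 5.1 is asked and the answer recorded at every 12-week contact, by telephone or on site, regardless of pain relief. Record the mode of each contact. The longest gap between scheduled AE enquiries then becomes 12 weeks for every subject in follow-up, and the option to omit visits is left as it is.

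For subjects who join late or return after a break, state that the look-back in item 5.1 applies at the first extension contact, of either mode, and reaches back to week 52.

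The cost is one extra question in a call that is already planned and one line of clarification for late entry. The reported late AE rate may come out slightly less favourable.

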**Table 2. Flow sheet of Visits/Assessments**

Study Visit Schedule for the initial 52-week study period:

week ( $\pm 7$ days) >>	<<No of tests	1	2	3, 5	4, 6	5, 6	7	8	9, 11, 13, 15, 17, 19	10, 14, 18	12, 16	20, 32	21, 23, 25, 27, 29, 31, 33, 35, 37, 39, 41, 43, 45, 47, 49, 51	22, 26, 28, 30, 34, 36, 38, 42, 44, 46, 50	24, 40, 48	52
SCREENING		x														
SURGERY, or week-5,6 screening for surgery						x	x	x								
LONG-TERM DBS in PAG/PVG (note 1)									x	x	x	x	x	x	x	x
TAPERING or STOPPING of PAIN MEDICATION(S)												x			x	
COMPREHENSIVE TESTING	4		x										x			x
ABBREVIATED TESTING	5										x				x	
TELEPHONIC INTERVIEW	40			x	x				x	x			x	x		
Sites																
Miami VA Medical Center (note 2)		x	x								x	x			x	x
Miami Project in Lois Pope Life Center (note 2)				x	x				x	x	x	x	x	x	x	x
University of Miami Hospital						x	x	x								
Study Therapy																
Targeting and lead placement	1						x									
DBS and lead connection	1							x								
DBS adjustment &-or sensing / possible 5 minute inactivation	9							x			x	x			x	x
General Assessments																
Informed Consent	3	#1	#2				#3									
Spinal Cord Injury history/Demographics	1	x														
Medical history, Brief medical examination	1	x														
Drug Abuse Screening Test (DAST)	1	x														
Folstein Mini-Mental State Examination (MMSE)	4	x											x			x
Beck Depression Inventory (BDI)	9	x									x	x			x	x
(PGIC)	44								x	x	x	x	x	x	x	x
Adverse Event assessment	52		x				x	x	x	x	x	x	x	x	x	x
Vital signs (BP, SpO2, temp)	12	x	x				x	x			x	x			x	x
Patient Diary on Medications	50	x	x	x	x				x	x	x	x	x	x	x	x
Qualitative exit interview	1															x
Neuro System Exams																
ASIA Neurological Exam	4	x											x			x
Tilt table response exam (note 3)	4		x										x			x
Patient Self-assessment of Autonomic Responses	38			x	x				x	x			x	x		
Autonomic Standards Assessment	9		x								x	x			x	x
Multidimensional Pain Inventory (MPI-SCI)	4		x										x			x
Quantitative sensory testing (QST)/Allodynia	4		x										x			x
ISCI Pain Basic Data Set / NPSI	25		x		x					x	x	x		x	x	x
Imaging																
Neuroimaging - MRI study	1						x									
Neuroimaging - CT study	1							x								
Electro-cardiogram (EKG)	1						x									
Chest x-ray	1						x									
Laboratory																
CBC, Comprehensive Metabolic Panel (including Mg + , Renal & Liver Function), PT/PTT	2		x					x								
Urine Pregnancy (note 4)	2		x					x								
HIV, Hep B, Hep C serology	1		x													

1 All General Assessments and Neurological System Exams, i.e., BDI, MMSE, QST, Pain (ISCI PBDS, NPSI, MPI-SCI), PGIC, during this period will occur prior to DBS adjustments.

2 Pain testing may take place at either site

3 Not required if determined subject can't tolerate it to completion

4 Urine pregnancy test for premenopausal women

## 12.7 Description of the "Stopping Rules" or "Discontinuation Criteria" for Individual Participants, Parts of Trial, and Entire Trial.

### A. Termination by the Participants

Participants may withdraw consent to participate in this study at any time by informing the Principal Investigator. No further procedures will be performed or information will be collected from participants that withdraw consent. Previously collected data and samples will be used for the study analysis.

### B. Termination by the Sponsor

The Sponsor may terminate the study at any time for any of the following reasons:

- Failure to enroll patients.
- Protocol violations.
- Inaccurate or incomplete data.
- Unsafe or unethical practices.
- Questionable safety of the study device.
- Administrative decision.

### C. Termination by the Principal Investigator:

The Principal Investigator may remove a subject from the study at any time for any of the following reasons (Note: If the PI removes a subject prematurely, the PI shall promptly provide the IRB/IEC and the Sponsor with a written statement describing why the study subject was removed prematurely).

- Onset of confounding neurological problems such as severe dysesthesia, severe neuropathic pain, or changing neurological level.
- Serious adverse event: discontinuation due to a serious adverse event.
- Lost to follow-up: the subject fails to return to the study site for scheduled visits and does not respond to attempts to contact.
- Withdrew consent: the subject decides to stop his participation for any other reason than an adverse event, or is unable to complete the study as described in the study protocol.
- Administrative: the Sponsor decides to terminate an individual subject or decides to discontinue the study due to general safety concerns.
- Protocol violation: anything that is a direct and significant violation of the clinical study protocol.

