## 10 RISK ANALYSIS

The rationale for unilateral or bilateral DBS implants is based on the potential benefits that may be produced. For participants with chronic SCI, the benefits anticipated from DBS include reduction or alleviation of neuropathic pain. A beneficial effect on autonomic dysreflexia is also possible, since PAG/PVG stimulation inhibits the types of nociceptive pain that elicit it.

The risks of the device implant surgery (to the participants) in this study are identical and no more than those associated with current DBS surgery for Parkinson's treatment. The risks include, but are not limited to, bleeding, transfusion, infection, sensory impairment, paralysis, speech arrest, stroke, seizure, intracerebral hemorrhage, coma, and/or death. The participants will be made aware of the risks in writing and in person. These participants will all be consented prior to entering the study.

To minimize surgical risks, exposure to general anesthetic, and additional stereotactic frame placement in one cranial procedure (as opposed to two separate) will be used to implant bilateral devices. This approach falls under the standard of care for DBS neurosurgery.

There is potential throughout the study of adverse events occurring related to the implant itself. These include but are not limited to, erosion of the device through the skin, migration or movement of the hardware in the brain, delayed infection of the device, battery failure, and/or mechanical failure of the device. These complications may necessitate further surgery to correct. However, it is important to note that the safety profile of this device and the surgical procedure is well established, and investigator(s) are well trained and have previously conducted several hundred identical implant procedures.

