### 13.3 Inclusion Criteria

- a) Age: 22 - 60 years old at last birthday;
- b) Diagnosis of traumatic SCI at or above the 12th thoracic segment (T12) that occurred >365 days;
- c) Neuropathic pain below the level of injury, as determined based on pain in an area with neurological deficit and described as burning, shooting, electric, stinging etc.

- d) The injury must have occurred at least 1 year prior to entering the study and participants must have experienced chronic pain for a minimum of six months.
- e) The disability must have a grade on the American Spinal Injury Association Impairment Scale (AIS) of ASIA-A, ASIA-B, ASIA-C or ASIA-D as determined by qualified examiners.
- f) Pain (neuropathic) of moderate severity or greater is present, when the patient is taking their routine pain medication, with a score of at least 4 on a numerical rating scale (range of 0 to 10).
- g) Participants who are on medications for other conditions, such as diabetes, will be considered as candidates for this study. The dose will be monitored throughout the trial. (They will be excluded if the drug is being used to treat epilepsy, Parkinson's diseases, or other brain degenerative diseases.)
- h) Participants will be allowed to utilize over-the-counter drugs such as NSAIDs, acetaminophen and aspirin. Their use will be documented in the weekly pain assessments. A list of "allowed" medications will be provided to study participants. After the surgery, patients will be allowed to take stay on the protocol if they take Tramadol (50-100 mg, 2 times a day for up to 2 weeks) as a rescue drug in addition to their stable medication.
- i) The patient must be taking pain medication to maintain a stable level of medication from 4 weeks before surgery to 12 weeks after (the primary endpoint), except on the day of surgery. On the day of the surgery, in the presence of a physician who can provide immediate backup pain control if needed, medications will be stopped until the acute effects of DBS on analgesia have been evaluated.
- j) The participant must be willing to comply with the protocol including all scheduled visits.
- k) Autonomic dysreflexia can be present but is not a necessary requirement. Autonomic dysreflexia will be defined as rise of systolic pressure by more than 30 mm Hg during noxious skin stimulation or when the bladder or bowel are full, or apparently spontaneously over a period of minutes
- l) Literate at 8th grade level or above.

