**13.5 Withdrawal Criteria:**

- a) Participants may withdraw consent to participate in this study at any time by informing the Principal Investigator. No further procedures will be performed or information will be collected from participants that withdraw consent. Previously collected data and samples will be used for the study analysis;
- b) The only anticipated circumstance under which the Principal Investigator would terminate a subject's participation is if information was obtained which made the subject ineligible for the study. The primary reason for this premature termination is to be indicated by selecting one of the following definitions:
  - Gradual deterioration in neurological status from incomplete to complete SCI, or change in ASIA grade to a more severe level: B to A, C to A or B, D to A or B or C;
  - Unresolved post-surgical wound infection;
  - Onset of confounding neurological problems such as severe dysesthesia, severe neuropathic pain or changing neurological level;
  - Serious adverse event: discontinuation due to a serious adverse event;
  - Lost to follow-up: the subject fails to return to the study site for scheduled visits and does not respond to attempts to contact;
  - Withdrew consent: the subject decides to stop his participation for any other reason than an adverse event, or is unable to complete the study as described in the study protocol;
  - Administrative: the Sponsor decides to terminate an individual subject or decides to discontinue the study due to general safety concerns;
  - Protocol violation: anything that is a direct and significant violation of the clinical study protocol.

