#### 14.5 Post Implantation Procedures & Follow-up

Procedures performed to evaluate the safety of the investigational procedures and to evaluate subject outcome for this study include:

- A. Beginning one week after surgery, participants will undergo follow-up assessments post-implantation:
  - i. Pain assessments every 2 weeks (ISCI basic pain data set, NPSI), starting on week 10, will assess for development of, or changes in neuropathic pain; more comprehensive pain testing (MPI quantitative sensory testing/allodynia) will take place on comprehensive testing visit weeks (20-week, 32-week, and 52-week).
  - ii. Autonomic Standards Assessment: on on-site visit weeks (BP, HR, sympathetic skin response) and on week 20, week 32, and week 52 (Tilt table response exam). Patient Self-assessment of Autonomic Responses occurs weekly starting on week 3, except on on-site visit weeks.
  - iii. QoL assessments: on on-site visit weeks, starting on week 12 (Beck Depression Inventory (BDI-1a)) and weekly, starting on week 9 (Guy/Farrar Patient Global Impression of Change (PGIC));
  - iv. ASIA motor and sensory assessments: on weeks 20, 32 and 52 to assess any improvement or deterioration in neurological function;
  - v. a qualitative exit interview with audio recording at 52 weeks, giving subject and investigators will be given the opportunity for open comments and questions concerning elements of the study.

- B. Follow-up assessments will take place either at the Miami VA Hospital or at The Miami Project to Cure Paralysis, Department of Neurological Surgery, for regular follow-up visits for 44 weeks post-surgery. At each visit, information will be collected regarding the safety of the treatment, the presence or absence of adverse side effects, and the efficacy of the therapy with respect to recovery of neurological functioning or the development of adverse effects.

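### The investigator may remove a participant from the study for events that the trial measures as outcomes, and nothing then requires pain or ASIA assessment to week 52

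*Combined protocol and SAP*

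**What the plan says.** Section 12.7C gives the power: "The Principal Investigator may remove a subject from the study at any time for any of the following reasons". Its list includes confounding neurological problems and an SAE. It also requires a prompt written explanation to the IRB and the Sponsor.

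Section 13.5 covers termination of participation. It says the only circumstance anticipated is "if information was obtained which made the subject ineligible for the study", and then lists the reasons to be coded. One is "Onset of confounding neurological problems such as severe dysesthesia, severe neuropathic pain or changing neurological level"; another is an SAE. Section 13.5 alone adds deterioration to complete injury or "change in ASIA grade to a more severe level".

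The same events are outcomes elsewhere in the plan. Under Section 14.5, pain assessments every two weeks "will assess for development of, or changes in neuropathic pain", and the ASIA exam is done "on weeks 20, 32 and 52 to assess any improvement or deterioration in neurological function". Section 15 names more pain as an example of a site-specific harm. It says such harms can be examined by switching stimulation off and, unless explained by special circumstances, lead to stopping the study treatment.

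Section 12.7D says that a patient whose stimulation is stopped or held constant is followed as planned while willing. It opens with the clearly successful case and does not mention removals under 12.7C.

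Appendix 1 follows reported events until they resolve or stabilize. Item 3.1 closes routine reporting of new events 30 days after the last voltage output. Item 4 requires reporting of post-study device-related SAEs and gives no end date. Section 17.4 examines the reasons for missing data and imputes by regression.

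**The concern.** Section 13.5 presents the reasons as newly found ineligibility, but most of them do not make anyone ineligible under Section 13.3. That section admits ASIA grades A to D and neuropathic pain of at least 4 on the 0 to 10 scale. A participant who moves from grade B to A, or whose pain becomes severe, still meets those criteria. What has happened is a bad outcome after treatment.

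If the removal power is used, scheduled observation ends in a participant who did badly, and ends because of it. Two things are then lost:

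- **The later neurological and pain course.** This includes the off-stimulation values that Section 15 relies on to judge whether a harm came from stimulation. ASIA is examined only three times after implant, so there is little on file from which to impute.
- **Routine collection of new adverse events.** Section 10 warns: "There is potential throughout the study of adverse events occurring related to the implant itself". Section 14.4 says that requests to have the device taken out are rare, so most removed participants would still carry it.

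With 12 participants, each one is 8% of the data (1/12), and the results are meant to show whether a larger study is warranted.

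**Working it through.** The plan gives no figure for expected removals, so there is none to reproduce. The gap is established from the text; the arithmetic only sizes its consequences.

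**1. Does any clause require scheduled assessment after removal?**

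| Clause | What it does | Requires pain or ASIA visits to week 52 after a 12.7C removal? |
|---|---|---|
| 12.6, 15 | One-year AE monitoring, in general terms | No; silent on removed participants |
| 12.7C | Written explanation of the removal | No |
| 12.7D | Follow-up when stimulation is stopped or held constant | Not stated; opens with the success case |
| 13.5 | Limits the anticipated circumstance to ineligibility | No |
| 15(a) | Stops treatment for site-specific harms | No |
| Appendix 1, items 2.2 and 3.1 | Follow existing events until resolved or stable | No; that event only |
| Appendix 1, item 4 | Post-study device-related SAEs are reported | No; no scheduled contact |
| 17.4 | Examines reasons for missing data, imputes | No |

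**2. Scheduled data lost.** On-site visits after implant are at weeks 12, 16, 20, 24, 32, 40, 48 and 52 (Section 15). ASIA exams are at weeks 20, 32 and 52 (Section 14.5). The removal weeks are assumptions. Telephone weeks are the weeks remaining to 52 minus the remaining visits (Table 2).

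| Removed after | Visits lost (of 8) | ASIA exams lost (of 3) | Telephone interviews lost |
|---|---|---|---|
| week 12 | 7 | 3 | 40 − 7 = 33 |
| week 20 | 5 | 2 | 32 − 5 = 27 |
| week 32 | 3 | 1 | 20 − 3 = 17 |

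**3. Routine reporting of new AEs.** Assume stimulation stops at removal in week w. Reporting under item 3.1 ends at w + 30/7, and the uncovered time is 52 − (w + 30/7).

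- w = 12: ends at week 16.3; 35.7 weeks uncovered; 35.7/44 = 81%.
- w = 20: ends at week 24.3; 27.7 weeks uncovered; 27.7/44 = 63%.
- w = 32: ends at week 36.3; 15.7 weeks uncovered; 15.7/44 = 36%.

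These shares do not apply to events reportable under item 4.

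**4. Effect on mean pain change.** This is a simulation, and all its inputs are assumptions: n = 12, earlier and late NRS change bivariate normal with mean 0 (no true effect) and SD 2, and correlation r from 0.3 to 0.7. The worst k participants are removed. Their late value is imputed by regression on their own earlier change, fitted on those who remain. There were 100,000 runs per setting, with Monte Carlo standard error about 0.002. The table shows the shift in mean late change; negative is a false improvement.

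| Removal driven by | k = 1 | k = 2 | k = 3 |
|---|---|---|---|
| Earlier change, already recorded | 0.00 | 0.00 | 0.00 |
| Equal mix of earlier and late change | −0.10 to −0.19 | −0.21 to −0.39 | −0.34 to −0.61 |
| Late change, unseen (bound) | −0.16 to −0.27 | −0.33 to −0.51 | −0.50 to −0.74 |

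The larger shifts go with the lower correlation. A separate run of 60,000 per setting agreed within 0.005. For scale, the standard error of a mean of 12 with SD 2 is 2/√12 = 0.58.

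**The case against.** The strongest reply is that this is discretionary text with several restraints around it. Section 13.5 says termination is anticipated only for ineligibility. Section 12.7C requires a written account. The neurological reasons are limited to confounding problems, and the list in 13.5 works partly as a set of reason codes. Section 12.7D states a default that stopping stimulation does not end follow-up, and Section 15 stops treatment rather than participation for site-specific harms. Read generously, the plan already intends most of what is asked for here. All of this stands, and it lowers the severity. It does not settle what happens after a 12.7C removal: 12.7D does not mention one, and 13.5 counts the trial's own outcomes as ineligibility.

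A reader might also infer that late implant events would go unreported altogether. The documents do not support that, because Appendix 1 item 4 covers post-study device-related SAEs without an end date. The gap is in other new events and in scheduled contact.

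Nor would the harm be hidden. The removal reason is recorded and explained in writing, AEs are listed (Section 17.1), and the triggering event is followed until stable. What is lost is the later course.

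Finally, an investigator would most likely remove someone for pain already seen, and pain is recorded every two weeks. In that case the bias in mean pain is about zero. This stands, so the pain figures cannot carry the point.

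**Conclusion.** The point holds as a gap in the text. Sections 12.7C and 13.5 allow removal from the study for measured outcomes, and no clause requires scheduled pain or ASIA assessment to week 52 afterwards. Routine reporting of new AEs outside Appendix 1 item 4 ends 30 days after last stimulation.

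The main loss is the later safety and neurological course. For removal after week 12, 20 or 32, it is 3, 2 or 1 of 3 ASIA exams and 81%, 63% or 36% of the post-implant weeks. The shares assume that stimulation stops at removal.

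It would be tempting to conclude that the pain result would be materially biased. The documents do not support that. The shift is about zero under the likeliest removal rule and grows only if removal tracks later, unseen worsening. It also rests on an assumed SD, correlation, removal rule and number removed. The efficacy analysis is descriptive, and no decision threshold is stated for such a shift to cross.

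Confidence is high for the gap in the text and lower for its consequences, because the frequency of removal is unknown. This is a cheap improvement of minor to moderate severity.

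**What to change.** 1. In Sections 12.7C and 13.5, make severe dysesthesia or neuropathic pain, changing neurological level, worse ASIA grade and SAE reasons to stop or adjust stimulation, not to leave the study. State that the follow-up sentence in 12.7D applies to them.
2. Follow every participant in whom lead insertion was attempted on the existing Table 2 schedule to week 52, off stimulation if needed, unless consent is withdrawn.
3. In Appendix 1 item 3.1, extend AE collection to the later of week 52 or 30 days after last stimulation.
4. In Section 17.4, add a simple sensitivity summary that counts discontinuation for these reasons as treatment failure.

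**Cost:** wording in four places. Each affected participant would attend 3 to 7 on-site visits and take about 17 to 33 telephone interviews (discontinuation after week 32 to after week 12), all already scheduled. The freedom to stop or adjust stimulation and the right to withdraw consent are unchanged. Observed results may be less favourable.
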